Effect of Iosartan on Mucociliary dysfunction in patients with Chronic Obstructive Pulmonary Disease (COPD) and Chronic Bronchitis

PROTOCOL

VERSION 5.0 DATE: February 1, 2019 NCT Number: NCT02416102

Principal Investigator:	[name] [name] Division of Pulmonary, Allergy, Critical Care, and Sleep Medicine University of Miami School Of Medicine [name] Office: [contact]

Sponsor:

[name] [name] Division of Pulmonary, Allergy, Critical Care, and Sleep Medicine University of Miami School Of Medicine [name] Office: [contact]

Funding:

Flight Attendant Medical Research Institute

Objectives

On this study we will test the hypothesis that inhibiting TGF-ß signaling with losartan in smokers and ex-smokers with chronic obstructive pulmonary disease (COPD) leads to increased Cl⁻ conductance through CaCC in vivo by assessing nasal potential difference (NPD), a surrogate for potential differences in epithelia of the lower airways and therefore an appropriate outcome variable for a proof of concept clinical trial, avoiding the long trial durations typical for COPD studies. NPD measurements will be done in the untreated cohort and repeated while giving 50 mg and subsequently 100 mg losartan for 4 weeks each. The study design will allow intra-individual comparisons of the effects of losartan on BK channel function as measured by Cl⁻ conductance through CaCC.

Background

Mucociliary clearance (MCC), a major airway host defense system, is dysfunctional in patients with smoking-associated lung diseases such as chronic bronchitis and COPD. Mucociliary dysfunction accounts for the clinical hallmarks of these diseases, namely chronic productive cough and recurrent respiratory infections. For appropriate MCC, motile cilia beat in a highly regulated airway surface liquid (ASL) that optimizes ciliary beat frequency (CBF) and efficiency and provides hydration to mucus. Airway epithelia use ion transport (absorption of Na⁺ and secretion of K⁺ and Cl⁻) to regulate ASL volume and composition to optimize MCC.

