We recently found that ATP-dependent, apical Cl⁻ secretion and ASL fluid regulation depend on the activation of apically expressed large conductance, Ca²⁺ activated and voltage-dependent potassium (BK) channels. By secreting K⁺, apical BK channels provide a driving force for apical Cl⁻ secretion via Cl⁻ channels, forming a so-called apical loop current. This BK function is critically important since inhibition of BK channels reduces ASL volume significantly (in the presence or absence of functional CFTR), thus shifting the focus of ASL volume regulation upstream from Cl⁻ channels to BK channels.

Increased airway TGF-ß1 expression and signaling is common in active cigarette smokers and ex-smokers with COPD. Our preliminary data show that TGF-ß1 and cigarette smoke exposure decrease BK activity and cause ASL volume depletion. We therefore propose that smoke exposure, via TGF-ß1 production, leads to apical BK channel dysfunction to cause ASL volume depletion and mucociliary dysfunction in smokers and ex-smokers with COPD. BK rescue is associated with increased ASL volume and CBF. Therefore, restoring ASL volume requires BK channel rescue or inhibition of TGF-ß signaling. Clinically used Angiotensin II Receptor Blockers (ARBs) are known to inhibit TGF-ß signaling and present a "low-hanging-fruit" approach (medication already in clinical use) for intervention in COPD. In a murine model, losartan has previously been shown to attenuate cigarette smoke-induced lung injury and to rescue lung architecture. Our preliminary data suggest that losartan partially rescues BK channel function leading to increased ASL volume and CBF in airway epithelial cells exposed to smoke. The long-term goal of this study is therefore to evaluate the effect of currently available and clinically useful TGF-ß1 signaling inhibitors on mucociliary function in individuals with smoke-associated airway diseases, such as chronic bronchitis and COPD.

This is a proof of concept, open label protocol to evaluate the effect of ARB on cigarette smoke-induced lung injury in smokers, ex-smokers with and without COPD, giving 50 mg and subsequently 100 mg losartan for 4 weeks

Study Population

Group I, COPD:

10 ex-smokers not treated with ARBs **with** evidence of fixed airflow obstruction by pulmonary function testing (PFT), decreased DLco **and** with the clinical diagnosis of chronic bronchitis.

Group II, non-COPD:

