20 active smokers not treated with ARBs **without** evidence of airflow obstruction by PFT and **normal** DLco but **with** the clinical diagnosis of chronic bronchitis.

Group III, lung healthy, life-time non-smoker:

20 never smokers not treated with ARBs **without** evidence of airflow obstruction by PFT, a **normal** DLco **and no** evidence of the clinical diagnosis of chronic bronchitis

Groups will be appropriately balanced considering COPD stage, smoking status, lung function and age.

Inclusion and Exclusion Criteria

Inclusion criteria

- Age between 35 and 75 years old
- ex-smokers (>10 pack-years of cigarette smoking) not treated with ARBs and with evidence of fixed airflow obstruction by pulmonary function testing (PFT), decreased DLco and with the clinical diagnosis of chronic bronchitis. Or

active smokers (>10 pack-years of cigarette smoking) not treated with ARBs **without** evidence of airflow obstruction by PFT and **normal** DLco but **with** the clinical diagnosis of chronic bronchitis.

Or

never smokers not treated with ARBs **without** evidence of airflow obstruction by PFT, a **normal** DLco **and no** evidence of the clinical diagnosis of chronic bronchitis

• Ability to understand and willingness to sign consent documents

Exclusion criteria:

- Current therapy with ACE inhibitor, intolerance to ARB
- Women of child bearing potential
- Regular use of NSAIDs or potassium supplementation, treatment with aliskiren, anticoagulation
- COPD exacerbation requiring treatment within 6 weeks
- Oral corticosteroid use within 6 weeks
- Significant hypoxemia (oxygen saturation <90% on room air), chronic respiratory failure by history (pCO₂ > 45 mmHg) and forced expiratory volume in 1 second (FEV₁) below 40%, clinical evidence of cor pulmonale

- Untreated arterial hypertension (systolic blood pressure >140 mm Hg, diastolic blood pressure > 90 mm Hg)
- Blood pressure less than 100 mm Hg systolic or 70 mm Hg diastolic at Screening visit and Visit 2.
- Cardiac, renal, hepatic (LFTs > 3x normal upper limit), neurological, psychiatric, endocrine or neoplastic diseases that are judged to interfere with participation in study
- History of renal artery stenosis
- Concomitant airway disorders other than COPD and chronic bronchitis, such as bronchiectasis and asthma (history and reversible airflow obstruction by ATS criteria)
- History of pulmonary malignancies, and any other malignancies in the last 5 years
- History of thoracic surgery.

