- Acute pulmonary exacerbation within 6 weeks from the Screening Visit.
- Subjects with no airflow obstruction by spirometry but with a decrease in DLco < 70% possibly indicating emphysema.
- Significant exposure to environmental tobacco smoke or atmospheric or occupational pollutants for the non-smokers group.
- Urine pregnancy positive test at the Screening Visit.

Treatment arms

Patients will be given four weeks of 50 mg of losartan daily and consequently an additional four weeks of 100 mg of losartan (divided in two doses of 50 mg twice daily). This higher losartan dose was used safely in other clinical trials (www.clinicaltrials.gov; search: losartan and COPD). At the end of each four-week period, participants will be re-evaluated. We will compare treatments using baseline measurements of each individual as his/her own control.

Study Drug:

Cozaar[®], the commercial form of losartan will be obtained from the UMHC Pharmacy and given to the subjects by the PI or study coordinators free of charges. FDA has granted IND exemption for this study. Study drug will be stored as per package instructions in a locked cabined on the research room at UMH 6th floor west room 607. Only the study team has access to this room. The storage area at the study center will be monitored by the staff for temperature consistency with the acceptable storage conditions.

The Investigator is responsible for maintaining accurate study drug accountability records throughout the study.

Each dispensing of study drug will be documented in the subject's study records and in the drug accountability log. Subjects will return all unused study drug for drug accountability. Study drug will be destroyed at the clinical site as per the Institution regulations.

Study Procedures

Once informed consent is signed, the subjects will have an initial visit during which they will have a physical exam (including vital signs), complete study questionnaires and PFTs. All study subjects will undergo the following procedures during a single visit:

History and physical examination will be performed including vital signs and body mass index (BMI) will be recorded.

Laboratory Samples: Urine will be collected for a pregnancy test if applicable and blood test for CMP and CRP will be drawn, if results are not available within 6 months of the Screening visit.

Urine cotinine levels will be measured at the time of study visits to assess smoking status (active or not).

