NPD measurement will be performed according to standard procedures. In this aim, we will use one side of the nose for the evaluation of the function of CFTR and CaCC by measuring the potential differences by initial blocking ENaC with amiloride, then using chloride free solution and isoproterenol to evaluate CFTR function, followed by ATP to evaluate CaCC function. In the other nostril, the same experiment will be repeated as mentioned above, except that after blocking ENaC with amiloride and perfusion with chloride-free solution the CFTR will not be stimulated with isoproterenol, but ATP will be used to maximize the CaCC signal. We will adjust the way of measuring the NPD for aim 2.2 depending of the results in aim 2.1.

TGF-ß and citokines will be measured using Leukosorb, a noninvasive sampling method of the nasal mucosa as previously reported. In addition, we will obtain a small amount of nasal epithelial cells to measure TGF-ß by qPCR.

Study Visits:

V1 (Screening Visit): This will be a single visit for the purpose of determining eligibility, obtaining informed consent, and recording the necessary data will include:

- Assessment of general health status and physical examination (incl. vital signs)
- Urine pregnancy test if indicated (female, child bearing age)
- Spirometry pre- and post-bronchodilators, DL_{co}, lung volumes
- Pulse oximetry
- Review of laboratory values, or if not available: venous blood sampling to assess for renal and liver abnormalities (then the measurements will be done within a week in an additional visit), CRP
- If inclusion criteria fulfilled and no exclusion criteria found:
 - Enrollment

- Completion of respiratory questionnaires (COPD only)
- Six minute walk test (COPD only)
- BODE index calculation

V2 (week 4): This visit (and the two following ones) will only done for the groups not treated with any ARBs. This visit will occur 4 weeks (\pm 4 days) after V1.

- We will again review laboratory values (CMP, CRP), repeat urine pregnancy test if indicated (female, child bearing age).
- The following procedures will be executed:
 - Completion of respiratory questionnaires (COPD only)
 - Six minute walk test (COPD only)
 - BODE index calculation
 - NPD measurement followed by nasal fluid recovered by Leukosorb filter paper and nasal cell collection for TGF-ß

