DSMB: the PI and the co-investigators will continuously monitor the study for side effects. If any AE or SAE occur, the physicians will assess the event and report them to the appropriate authorities if needed as per Good Clinical Practice. Subjects might be withdrawn from the study if they experience intolerance to the study medication and/or the NPD testing. Furthermore, a COPD exacerbation will be a reason for subject withdrawal. We expect few dropouts for exacerbation given the three-month duration of the study. IND: because this study will use a medication released on the market but not for this indication, we will file an IND with the FDA for use of losartan in this population. Given our experience with INDs and the long experience with use of losartan, we do not believe that this will be a hurdle for the trial.

Assessment of efficacy

N/A

Statistical analysis

Differences between groups and doses will be analyzed with regression analysis. Multivariate analysis will be done to evaluate differences in the tests results between different groups and correlations between different measures will be examined using the Pearson's correlation coefficient. Biostatistics Collaboration and Consulting Core services will be used on a fee for service

Risks to Subjects

Potential Risks: All procedures are performed during this study are routine clinical procedures and are associated with minimal risks.

Pulmonary Function Testing is a routine clinical procedure with few risks. Patients are coached to make repeated forceful breathing efforts. The subjects might have chest soreness. Unusually, subjects may become lightheaded during these efforts. The risk is minimized by having the PFT done in a sitting position.

NPD measurement: is a non-invasive method with minor risks, which are swallowing and aspiration of the solution used for rinsing the nose. Having the patient bending the head

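### The V4 procedure list omits the nasal potential difference measurement that the 50 mg comparison needs; secondarily, the analysis text does not carry over the own-control comparison

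*Combined protocol and SAP*

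**What the plan says.** **Where NPD is measured.** Objectives says NPD is done untreated and "repeated while giving 50 mg and subsequently 100 mg losartan for 4 weeks each". In Appendix I the NPD row is marked at V2, V4 and V6. Under Study Visits, the V2 and V6 lists each contain an item for NPD followed by nasal fluid and cell collection. The V4 list contains the nasal fluid and cell collection but no NPD. V4 is also the visit at which the 50 mg period ends and the twice-daily supply is handed out.

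**How doses are to be compared.** Objectives: "The study design will allow intra-individual comparisons of the effects of losartan on BK channel function". Treatment arms: "We will compare treatments using baseline measurements of each individual as his/her own control".

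**How the data are to be analysed.** Statistical analysis: "Differences between groups and doses will be analyzed with regression analysis". The section adds multivariate analysis for differences between groups, without defining it, then Pearson correlation between measures, and the use of a biostatistics core. It names no pairing, change from baseline, baseline covariate, subject effect or rule for several visits per person. Assessment of efficacy is marked not applicable, and no other section supplies a model.

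**Group sizes.** Study Population lists "10 ex-smokers not treated with ARBs", "20 active smokers not treated with ARBs" and 20 never-smokers.

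**The concern.** The outcome of this proof-of-concept study is the NPD response, and the intervention is a two-step dose sequence. NPD at the end of the first step is the only scheduled measurement that can separate the effect of 50 mg from the effect of the full sequence. A coordinator working from the V4 list would not do it, and it cannot be recovered once the subject has moved to the second step.

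The secondary issue concerns the analysis. One sentence puts a between-person factor (group) and a within-person factor (dose) into the same unspecified regression. These need different error terms. Ignoring the within-person correlation makes pooled group tests too liberal and, at moderate or high correlation, costs power for the dose contrast. The plan's stated intention is a within-person comparison, but the section an analyst would follow does not say so.

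**Working it through.** **1. NPD by visit, set side by side**

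| Source | V2 (untreated) | V4 (end of 50 mg) | V6 (end of 100 mg) |
|---|---|---|---|
| Objectives | yes | yes | yes |
| Study Visits | yes | **not listed** | yes |
| Appendix I | yes | yes | yes |

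Three contrasts are possible with all three values: V4−V2 (50 mg), V6−V2 (full sequence) and V6−V4 (dose step). Without V4, only V6−V2 remains, and the dose term in the regression reduces to before versus after. V6 doubles as the early-termination visit, so a subject who stops during the first period might supply an NPD value after 50 mg. That would be a selected few and would not replace a scheduled measurement. Nasal fluid, questionnaires and walk test are still collected at V4, so the loss is confined to NPD.

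**2. What hangs on the unspecified regression**

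The documents give no alpha, power, SD or within-person correlation, so there is no figure of the plan's own to reproduce. Assumptions: two-sided 5%, compound symmetry, ICC ρ = 0.1/0.3/0.5/0.7, groups 10/20/20, and visits entered as independent rows with group and visit terms.

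*Group comparison pooled over m visits.* The true variance exceeds the assumed variance by about 1 + (m−1)ρ. The actual size is therefore about 2[1 − Φ(1.96/√(1 + (m−1)ρ))]. For m = 3 and ρ = 0.5 the factor is 1 + 2 × 0.5 = 2, and the size is 2[1 − Φ(1.96/1.414)] = 0.166. Simulation gives:

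| False positives, % (ICC 0.1/0.3/0.5/0.7) | Three visits | Two visits |
|---|---|---|
| Group I versus Group II | 7.4/12.2/16.9/21.2 | 6.1/8.6/11.1/13.5 |
| Three-group F test | 8.2/15.5/22.6/29.4 | 6.5/10.1/13.6/17.4 |

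A single-visit group test, and a group test on change from V2, both stay at 5%.

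*Dose contrast.* Treating visits as independent overstates its standard error by 1/√(1−ρ) = 1.05/1.20/1.41/1.83. Take the COPD group (n = 10) and a V2-to-V6 change that a paired test finds with 80% power. That change is 0.996 SD of the paired difference, with half the effect at 50 mg when there are three visits. The independent-rows analysis finds it with power of about 83/75/60/34% (three visits) or 82/73/58/32% (two visits). Paired power is held at 80% at each ICC, so the raw effect is not constant: 0.996 × √(2(1−ρ)) = 1.34/1.18/1.00/0.77 SD. The series compares two analyses at each ICC. It does not show the loss for one fixed losartan effect.

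*Correlations.* Pearson pooled over three visits with n = 10 has 5/7/11/17% false positives if both measures share the same ICC, and 5% if one of them has ICC 0.

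**The case against.** On the visit list, the natural defence is that Objectives and Appendix I agree, so the V4 list is a drafting slip that sites would correct from the table. That may be so. But the V4 list is the operational text for that visit, and nothing in the protocol ranks one source above another. Nor is Appendix I a clean reference: it dates V4 at 8 weeks after V2, whereas Study Visits has V2 at week 4 and V4 at week 8.

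On the analysis, the case against is strong. Treatment arms already states that each person is his or her own control, which says how treatments are compared. Regression can include a change score or a mixed model, multivariate analysis could be meant to cover repeated measures, and a biostatistics core is to be involved. A reader might infer from the analysis section that visits will be analysed as independent observations, or that the plan contradicts its own-control design. The documents support neither reading. Independent rows are never mentioned and would not fit Treatment arms, and pooling a group comparison over untreated and treated visits is not described anywhere. What stands is an omission: the model is not named, and no rule is given for correlations with several visits per person.

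A reader might also count the unnamed nostril sequence as part of the error. NPD measurement describes a second sequence in which "the CFTR will not be stimulated with isoproterenol, but ATP will be used to maximize the CaCC signal", and allows the method to be adjusted for a later aim. Naming the sequence to be analysed would be useful, but it is optional detail, as are the choice of degrees-of-freedom method and coding dose as taken.

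**Conclusion.** The visit inconsistency is an error as written. The V4 list conflicts with Objectives and Appendix I, and if it is followed no 50 mg NPD contrast can be estimated. This conclusion rests on the text alone and needs no assumption.

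The analysis gap is real but secondary, and its harm is conditional. If visits were analysed as independent rows, pooled group tests over three visits would have roughly 7–30% false positives across ICC 0.1–0.7. The dose contrast in the COPD group would lose little power at ICC 0.3, much at 0.5 and above, and none at 0.1. These figures depend on an assumed ICC, alpha and correlation structure, and on an analysis that the plan does not describe. The likely readings, change from baseline or single-visit comparison, are valid. This part therefore calls for clarification; it is not evidence of an invalid analysis.

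**What to change.** **Visit list.** Reconcile the V4 list under Study Visits with Objectives and Appendix I. If the 50 mg NPD comparison is intended, V4 must list NPD. If it is not, the 50 mg NPD comparison has to come out of Objectives, Appendix I and the analysis of doses.

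**Analysis text.** Add, for example: *Dose effects on NPD will be analysed within person, as change from V2 or by a linear mixed model with a random subject effect, group, dose and, for groups with on-treatment NPD, group-by-dose. Correlations will use one value per subject (baseline or change).* The qualification on group-by-dose is needed because Recruitment Methods gives 30 subjects for the treatment phases, which equals 10 + 20. On one possible reading, never-smokers have only an untreated NPD, and the full interaction would then have empty cells.

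**Cost.** One corrected list and a short paragraph describing a standard analysis. No data are needed beyond those Appendix I already schedules. The downside is slightly more analysis text and less favourable p-values for any group comparison pooled over visits.

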 - Subjects will be provided with a 4-week supply of 50 mg losartan for daily use (first dose given in clinic; observation with blood pressure monitoring for 2 hours).

V3 (week 5 ± 4 days):

Telephone visit to follow up on symptoms and tolerability of medication.

V4 (week 8 ± 4 days):

- The following procedures will be executed:
 - Monitor for adverse events.
 - Completion of respiratory questionnaires (COPD only)
 - Six minute walk test (COPD only)
 - Venous blood sampling to assess for renal and liver abnormalities and CMP, CRP
 - Urine pregnancy test (if applicable)
 - BODE index calculation
 - Nasal fluid recovered by Leukosorb filter paper and nasal cell collection for TGF-ß
 - Subjects will be provided with a 4-week supply of 50 mg losartan for twice daily use (100 mg)

V5 (week 9 ± 4 days):

Telephone visit to follow up on symptoms and tolerability of medication.

V6 (week 12 ± 4 days) or Early Termination Visit:

- We will draw laboratory (CMP, CRP). Repeat pregnancy test if indicated (female, child bearing age).
- The following procedures will be executed:
 - Monitor for adverse events.
 - Completion of respiratory questionnaires(COPD only)
 - Venous blood sampling to assess for renal and liver abnormalities and CMP, CRP
 - Urine pregnancy test (if applicable)
 - Six minute walk test (COPD only)

- BODE index calculation
- NPD measurement followed by nasal fluid recovered by Leukosorb filter paper and nasal cell collection for TGF-ß

Unscheduled visit (up to 2 visits) will apply if there is a need to repeat study procedures.

Subjects are allowed to be re-screened one time as per PI discretion.

Specimen Banking

Not applicable.

Data Management

Data collected will include demographics, clinical symptoms, health-related quality of life, and pulmonary function test data. Samples to be collected include NPD measurement followed by nasal fluid and cell collection for TGF-ß. We will obtain blood for safety reasons (liver and renal function) and for evaluation of an inflammatory marker. No personal identifiers will be collected and each patient's data will be coded.

Safety Reporting

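### The planned comparison between doses cannot be read as a dose effect, because 100 mg always follows 50 mg and comes with a change in intake frequency

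*Combined protocol and SAP*

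**What the plan says.** The analysis text on dose is one sentence in the Statistical analysis section: "Differences between groups and doses will be analyzed with regression analysis". It names no period or time term, no assumption about drift, and no limit on how a difference between doses will be interpreted.

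The dosing sequence appears in several places and its order is always the same. Treatment arms: "Patients will be given four weeks of 50 mg of losartan daily and consequently an additional four weeks of 100 mg of losartan", the second step being "divided in two doses of 50 mg twice daily". The V4 entry under Study Visits dispenses 50 mg tablets for twice-daily use, which confirms the change in frequency. Objectives: "NPD measurements will be done in the untreated cohort and repeated while giving 50 mg and subsequently 100 mg losartan for 4 weeks each".

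The comparator is the subject's own baseline: "We will compare treatments using baseline measurements of each individual as his/her own control" (Treatment arms). Background adds: "This is a proof of concept, open label protocol". No randomised order, washout, placebo or parallel dose arm is described.

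On who is dosed, the V2 entry under Study Visits says "This visit (and the two following ones) will only done for the groups not treated with any ARBs". Study Population defines all three groups as not treated with ARBs.

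**The concern.** A regression with a dose term will print a coefficient for 100 mg against 50 mg, and readers will take it for the effect of doubling the dose. In this design it is the mean change from one visit to the next. That change also contains whatever happens with calendar time, with a further period on the drug, and with moving from one intake a day to two. The last of these may alter the time since the last dose when NPD is measured, although the protocol does not say whether NPD depends on that.

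The stakes are interpretive. With no concurrent control, a rise from baseline to 50 mg to 100 mg would be the most persuasive pattern this study could show for a drug effect. Longer exposure or simple drift would produce the same pattern.

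**Working it through.** The protocol gives no alpha, SD, effect size or power for any dose comparison, so there is no stated figure to reproduce. Two checks follow.

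**1. What the data can identify**

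Inputs: NPD occasions V2 (0 mg), V4 (50 mg) and V6 (100 mg), taking NPD at V4 as Appendix I marks it; one order for all dosed subjects; 30 subjects in the treatment phases (Recruitment Methods).

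Write the outcome of subject i as a subject effect plus β50·D50 + β100·D100, and let π4 and π6 be the period effects at V4 and V6. With a single order, D50 is the same column as the V4 indicator and D100 the same as the V6 indicator. The expected mean of V6-V4 is therefore

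(β100 − β50) + (π6 − π4),

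and only the sum is estimable.

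- Subject effects and two dose indicators: 30 + 2 = 32 columns, rank 32. Step-to-step changes are estimable.
- Adding two period indicators: 34 columns, rank still 32. The 100-minus-50 mg contrast is not estimable.
- Intakes per day (0, 1, 2) against dose (0, 50, 100): correlation 1.00.
- Cumulative mg (0; 50×28 = 1,400; 1,400 + 100×28 = 4,200) against dose: correlation 0.98.
- Weeks since V2 on the Study Visits timing (0, 4, 8) against dose: correlation 1.00. On the Appendix I timing (0, 8, 12) it is 600/√(5,000 × 74.67) = 0.98. There, a straight-line time term could be separated from dose only by assuming that both effects are linear. The aliasing with period indicators holds under either timing.

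To locate the cause, and not as a proposal: if half the 30 subjects had the reverse order, the rank would rise to 33 and the contrast would become estimable, given no carryover. Intake frequency would still be tied to dose.

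**2. How often drift alone would look like a dose difference**

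The drift sizes and the two-sided 0.05 level are assumptions. Let k be the V4-to-V6 drift in units of the SD of the paired V6-V4 difference, with a true dose effect of zero. The paired t statistic is then noncentral t with n − 1 degrees of freedom and noncentrality k√n, and it rejects beyond ±t(0.975, n − 1). For n=10 and k=0.25, the critical value is 2.262 and the noncentrality is 0.25 × √10 = 0.791, giving 10.9%.

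| n | k = 0 | k = 0.1 | k = 0.25 | k = 0.5 |
|---|---|---|---|---|
| 10 (Group I) | 5% | 5.9% | 10.9% | 29.3% |
| 20 (Group II) | 5% | 7.1% | 18.6% | 56.5% |
| 30 (treatment phases) | 5% | 8.3% | 26.3% | 75.4% |

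The same calculation applies to drift between V2 and V4. NPD is first measured at V2, so each subject has one untreated value and the study cannot estimate its own drift.

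**The case against.** **The plan claims no dose-response.** This is correct. The hypothesis in Objectives is that losartan raises chloride conductance, and Treatment arms compares each subject with baseline. A reader might infer that the authors intend a dose-response conclusion, but the documents do not say so. What stands is that differences between doses are a named target of analysis and nothing limits their reading.

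**The regression is full rank as planned.** This is also correct. A reader might infer from the aliasing that the model cannot be fitted or that nothing about the 100 mg step can be estimated. That goes too far: the rank falls short only when period terms are added, and the plan names none. The within-subject changes are estimable; their attribution to dose is not.

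**The rejection rates are not properties of this trial.** Agreed. No drift figure appears in the protocol, and at 0.1 SD the inflation is small. The table shows sensitivity only. The aliasing does not depend on it.

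**The group comparison might rescue the dose effect.** It does not, because every dosed group follows the same order. If Group III is not dosed, no separate follow-up NPD schedule for untreated subjects is described, and never smokers would be a weak control for time.

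**Some V6 values may be taken at 50 mg**, because early terminations follow the V6 procedures. Those subjects left early, so they cannot credibly separate dose from time.

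**A proof-of-concept study need not separate doses.** That is reasonable, and it is why only the analysis text needs to change.

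**Conclusion.** The point holds as a limit on interpretation. Dose is fully aliased with period and intake frequency and closely tied to prior exposure, and nothing elsewhere in the protocol repairs this. V6-V4 can be estimated, but it is a dose effect only under untestable assumptions of no time trend, no carryover and no frequency effect. V4-V2 and V6-V2 are uncontrolled in the same way with respect to time.

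The size of any distortion is unknown. On the assumed drifts, false dose differences range from near nominal (6% at n=10, 0.1 SD) to 75% (n=30, 0.5 SD). No single value in that range should be quoted as the trial's error rate.

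Two things in the documents are unsettled. The V4 list under Study Visits omits NPD and places V4 at week 8, which is four weeks after V2; Appendix I marks NPD at Visit 4 and places it 8 weeks after V2. If the Study Visits list governs, there is no scheduled NPD value at 50 mg at all. Whether all three groups are dosed is also unclear: the group definitions suggest so, but the 30 in Recruitment Methods equals Groups I and II (10 + 20), and Objectives names only smokers and ex-smokers.

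**What to change.** Before the analysis text is changed, reconcile Study Visits with Appendix I on whether NPD is done at V4 and when V4 and V6 fall, and state whether Group III is dosed.

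Then keep the design and replace the dose regression wording with prespecified within-subject changes:

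- V4-V2: change after the 50 mg step.
- V6-V2: change after the full sequence.
- V6-V4: descriptive only, not to be reported as a dose effect or dose-response.

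State that V4-V2 and V6-V2 are uncontrolled changes from baseline that cannot be separated from time. Record the clock time of the last dose at each on-treatment NPD, and carry out these NPDs at a similar interval after it.

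The cost is a few sentences of analysis text, one case report form field and some care in scheduling. The downside is giving up any dose-response claim.
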